3. Prepare for a larger RCT, the focus of which will be determined by the results from the pilot study. If one intervention demonstrates a clear superiority, it will be utilized in an RCT comparing it with usual care. If the effect size between groups is small to moderate, a larger RCT will be undertaken comparing the two interventions with a one-year follow up to determine differential effectiveness over time and moderators of effectiveness such as age, gender, alcohol dependence level and goal selection.

5. Study Design

This study will consist of three phases. Phase I will focus on developing the AI chatbot version of Step Away, improving the Step Away app and developing procedures for the pilot study, including evaluating the different program elements using an expert panel. Phase II will entail a feasibility study that will contrast the Step Away chatbot with the Step Away app and an assessment and feedback-only app (the first step of the Step Away app but nothing else) utilizing a randomized, controlled study design. One hundred and fifty participants who are 18 years of age and older who screen positive for unhealthy alcohol use will be recruited throughout the U.S. with Facebook and Google ads. All participants will complete an online, baseline research assessment and a follow-up at 4 months, allowing a minimum of 3 months of intervention use. Three months of intervention use will allow enough time for participants to utilize all aspects of the intervention system (the set-up phase), extended exposure to the daily assessment and weekly feedback functionality and provide a mid-length follow up period. Data from the app and chatbot usage will be continually uploaded to a secure server to determine usage and treatment fidelity information for each intervention. In addition, 10 participants in the chatbot and app conditions will be interviewed based on their degree of engagement with each intervention to obtain their perspectives on each intervention's usefulness and barriers to engagement. (At the 4-month follow-up, all participants will be given the Substance Abuse and Mental Health Services Administration's (SAMHSA) national treatment locator helpline to identify treatment services in their area.) Phase III will focus on quantitative and qualitative data analysis, manuscript development, conference presentations, revisions to StepAway intervention based on findings

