from this study, and design of a large-scale follow up trial to test the effectiveness of the improved intervention.

6. Participant Enrollment and Withdrawal

Participant Inclusion Criteria

Participants will be eligible to participate in the study if they:

- Are 18 years or older
- Have an iPhone or Android phone
- Are a U.S. resident
- Are not in another form of alcohol treatment
- Are actively drinking in the past 3 months
- Have English language proficiency
- Are not using another mHealth alcohol intervention
- Score on the USAUDIT between an 8 to 24 for males under 65
- Score on the USAUDIT between a 7 to 24 for females and males over 65 on the USAUDIT
- Electronically sign the consent form

For the interviews, from back-end data capture we will determine high and low users by the amount of time they spend using the app or the chatbot. High utilizers will be selected from amongst those participants in the top third of each intervention's use (based on total frequency and duration of use) and low utilizers will be selected from those in the bottom third for each intervention. Only participants in either the app or the chatbot intervention groups will be randomly selected to be interviewed.

Participant Exclusion Criteria

Participants will be excluded from participating if they indicate they are:

- more than 30 days abstinent at baseline
- in alcohol or drug abuse treatment currently
- pregnant or nursing
- having a moderate to severe level of alcohol use disorder, defined as having a score of 25 or higher on the USAUDIT
- unwilling or unable to complete follow-up assessment
- not residents of the U.S.
- unable to read or text in English

Recruitment and Enrollment

Participant recruitment will be conducted through Facebook advertisements. The advertisements will provide a link to the study website which will describe the study and provide a link to the prescreen survey. Facebook analytics will be reviewed weekly by the graduate research assistant and project manager. Analytics will be reviewed on each of the ads for which ads are more successful at recruiting interested participants and the demographics the ads are more successful at recruiting. These analytics will inform how to alter advertisements if the sample being recruited is largely one race or gender. Recruitment will begin in June 2020 and will end when the target sample is reached.

Prescreen

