- The treatment history section of the Form 90 will be modified to be administered online at baseline and follow-up, to gather lifetime treatment history, self-help attendance, and treatment use.
- Readiness to Change. We will utilize the Readiness to Change Treatment Version (RCQTV), which RCQTV has been shown to have solid reliability and validity and has been modified for individuals contemplating or engaged in treatment for alcohol problems.

Follow-Up

The US AUDIT, TLFB, SIP-R, and Readiness to Change questionnaires will be used for the follow-up assessments. In addition, those in the app and chatbot groups will be asked to complete the System Usability Scale to assess their perceptions of the interventions' usability. The follow-up survey will be sent to participants at 4 months post-enrollment.

Interviews

Interviews will be conducted after the completion of the follow-up survey. Interview questionnaires will focus on users' experiences with the app or the chatbot. These interviews will be conducted over the phone.

8. Assessment of Safety

Several safety measures will be put in place to ensure the safety, comfort, and confidentiality of all participants. Care will be taken to inform potential participants fully before they consent to participate about all potential risks that may arise from their participation. The two most important aspects of participant protection in the proposed work are assuring the adequacy of informed consent (including full disclosure of all potential risks) and protecting confidentiality. To minimize risk, we will clearly explain all procedures to participants in our informed consent documents and clearly outline safeguards for confidentiality implemented in the study. Further, in order to protect their confidentiality, all participants will be encouraged to set a password to access their smartphone home screen.

Also, a Data Safety Monitoring Board (DSMB) will be convened in Year 1 of the project and will include the following two members with expertise in psychology, behavioral health, and

research ethics. The DSMB will meet twice during each year of the project to review the status of the project.

9. Statistical Considerations

All randomized study participants who complete both the baseline and follow-up surveys will be the primary population for the analysis. Three subgroups will be analyzed: the app group, the chatbot group, and the delay group.

Outcomes, Statistical Methods, and Statistical Analyses

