All outcomes will be presented using descriptive statistics. Binary and categorical variables will be presented using counts and percentages. SPSS 27 will be used for all statistical analyses.

Research Question 1: Do participants reduce their alcohol consumption more when using the app or the bot?

Hypothesis 1: Participants using either the app or bot will show a significantly greater reduction in alcohol consumption and alcohol related problems than participants in the delay group.

Method: Repeated Measures Anova

Baseline and Follow-up data from the Alcohol Use Disorder Identification Test (USAUDIT), Short Inventory of Problems-Revised (SIP-R), Readiness to Change Questionnaire (RTCQ), and Timeline Followback (TLFB) will be compared between app, chatbot, and delay groups. Consumption data used from the TLFB will include drinks per day, percentage of days abstinent, and heavy drinking days. Average drinks per day will be calculated from the reported last 14 days of drinks. Percentage of days abstinent will be calculated as the percentage of days in the recent 14 days that participants reported 0 drinks. Heavy drinking days will be calculated as the number of days in the past 14 days that participants report drinking more than 3 drinks if they are an assigned female at birth or 4 drinks if they are an assigned male at birth. Repeated measures ANOVA will be ran to identify if there is an interaction between time and group. An interaction would indicate a significant difference between app, bot, and delay groups in the difference of their baseline and follow-up drinking data.

Research Question 2: Do participants utilize the app and bot differently?

Hypothesis 2: Participants in the bot group will utilize the intervention significantly more than the app group due to the intervention's conversational interface.

Method: Independent sample t-test

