The eIC will contain all elements of a paper informed consent, will be written at an 8th grade or below reading level, and will include questions to gauge the participants understanding of the project purpose, risks, key study elements, and their right to withdraw without penalty, at any time throughout the study. Incorrect answers to questions related to the eIC elements will highlight areas where participants may need further explanation and will prompt a call from study staff to answer questions. Participants can also request a call to discuss the content of the consent prior to electronically signing. It should be noted that OHRP permits electronic signatures if such signatures are legally valid within the jurisdiction where the research is to be conducted (in this case, Alaska). [name] will discuss all plans for using eIC with UAA's IRB before finalizing the eIC development, to assure it complies with institutional, state and federal regulations.

After completion of informed consent, participants will complete baseline assessments via the website. Following baseline assessment completion, participants will be randomly assigned to either chatbot or app versions of StepAway, or a waitlist to app, using a blinded, computer-generated random assignment code. This process will be repeated until at least 50 eligible participants are enrolled in each study arm.

In addition to the eIC that each enrolled participant completes at the outset of the study, each participant who agrees to participate in an interview will be provided with additional consent specific to the interview. As these will be done over the phone with participants who live across the United States, verbal consent will be requested and documented.

Participant and Data Confidentiality

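### The only analysis set named is people who return the 4-month survey, and the plan gives no way to judge how far the between-group result depends on those lost

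*Combined protocol and SAP*

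**What the plan says.** - **Analysis set.** Section 9 (Statistical Considerations) opens with: "All randomized study participants who complete both the baseline and follow-up surveys will be the primary population for the analysis". No second population is named.
- **Order of events.** Section 10 (Consent Procedures and Documentation) states: "Following baseline assessment completion, participants will be randomly assigned to either chatbot or app versions of StepAway, or a waitlist to app". Section 7 (Follow-Up) adds: "The follow-up survey will be sent to participants at 4 months post-enrollment". Everyone randomised therefore has a baseline, and there is one follow-up.
- **Method.** For Research Question 1: "Repeated measures ANOVA will be ran to identify if there is an interaction between time and group". Research Question 2 uses t-tests on utilisation. Research Question 3 uses a mediation analysis of utilisation and change in drinking.
- **Retention.** Section 6 excludes people who are "unwilling or unable to complete follow-up assessment". No expected loss is given.
- **Use of the result.** Aim 3 in Section 4 has two branches: "If one intervention demonstrates a clear superiority, it will be utilized in an RCT comparing it with usual care", and "If the effect size between groups is small to moderate, a larger RCT will be undertaken comparing the two interventions".

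**The concern.** Randomisation makes the arms comparable when people are assigned. A rule that keeps only those who return a survey four months later can undo this if the reasons for not returning it are linked to drinking and the amount of loss differs between arms. The confidence interval does not reflect that error.

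The documents make such loss plausible, though they do not show it. Section 3 names sustaining engagement as a limitation of health apps. Hypothesis 2 predicts that engagement will differ between chatbot and app. The control arm waits three months for the app.

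At stake is the between-group result on drinking, which Aim 3 uses to decide which larger trial to run. Hypothesis 3 has the same exposure because change in drinking is its outcome. Hypothesis 2 need not have it, because Section 7 says usage data upload continually to a server.

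**Working it through.** **What is missing.** The analyses in Section 9 are a repeated measures ANOVA, t-tests and a mediation analysis. With two time points, the ANOVA needs both values for each person. Nothing in the section covers those lost, and it refers to no plan elsewhere.

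**Size of the bias.** The plan has no figure to reproduce. These inputs are all assumptions except the 50 per arm, which is the plan's target:

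- no true effect; SD 1 at both times
- baseline/follow-up correlation r of 0.5 or 0.7
- probability of loss logistic in drinking, slope 1 per SD (0.5 as a weaker case)
- loss of 25% against 15% for chatbot versus app (either way round), and 25% against 10% as a wider gap

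In each arm, with loss q and gap g (mean change of those lost minus mean change of completers), the completer mean equals the full mean minus q × g. The bias is therefore −(q1 × g1 − q0 × g0). As a check, for r = 0.5, loss depending on change and 25% against 10% lost, the gaps are about 0.85 and 0.90 SD: 0.25 × 0.85 − 0.10 × 0.90 = 0.1225. The simulated bias (2,000,000 per arm) is 0.122 SD.

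Bias of the completer change comparison at slope 1, in SD (negative favours the arm that loses more):

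| Loss depends on | 25% v 15%, r 0.5 | 25% v 15%, r 0.7 | 25% v 10%, r 0.5 | 25% v 10%, r 0.7 |
|---|---|---|---|---|
| Baseline drinking | +0.042 | +0.024 | +0.06 | +0.037 |
| Follow-up drinking | −0.040 | −0.025 | −0.061 | −0.036 |
| Change | −0.081 | −0.064 | −0.122 | −0.095 |

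At slope 0.5, chatbot versus app falls to about 0.01 to 0.05 SD. With 25% lost in both arms and the same mechanism, the bias is zero.

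**Against sampling error.** Completers are 50 × 0.75 = 37.5 and 50 × 0.85 = 42.5. The standard error of the difference in change is √(2(1 − r)) × √(1/37.5 + 1/42.5):

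- r = 0.5: 1.000 × 0.224 = 0.224 SD
- r = 0.7: 0.775 × 0.224 = 0.174 SD

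The ratios run from 0.024/0.174 = 0.14 to 0.064/0.174 = 0.37. By the normal approximation, a nominal 5% two-sided test of that contrast would reject in about 5.2% (1 − Φ(1.96 − 0.14) + Φ(−1.96 − 0.14)) to 6.6% (the same with 0.37).

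**Would a mixed model cure this?** With two time points and a shared baseline mean, the likelihood splits into the baseline distribution and follow-up given baseline. Only completers inform the second part, so the arm effect equals that of ANCOVA on completers. On one simulated trial both gave 0.2051673. At 25% against 10% loss and slope 1, absolute bias in SD is:

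| Loss depends on | Change comparison (r 0.5; 0.7) | ANCOVA or model (r 0.5; 0.7) |
|---|---|---|
| Baseline drinking | 0.06; 0.037 | 0.00; 0.00 |
| Follow-up drinking | 0.061; 0.036 | 0.094; 0.065 |
| Change | 0.122; 0.095 | 0.094; 0.082 |

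ANCOVA had lower root mean square error in all six cases (for example 0.207 against 0.227 for follow-up-dependent loss at r = 0.5). That gain comes from baseline adjustment, not from using those lost.

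**The case against.** - **It is a small pilot with a qualitative decision rule.** This stands as to weight: the shifts are well below one standard error. It does not justify leaving the selection unexamined, because the plan tests between-group differences and carries them into Aim 3.
- **Unwilling people are excluded at entry.** That screens stated intention. It does not prevent later loss.
- **Loss may not differ by arm.** This stands. The documents give no loss rate and no evidence of a difference, and with equal loss and the same mechanism there is no bias. That is why reporting loss by arm is part of the fix.
- **Changing the primary analysis would not help.** This largely stands. Calling the set all-randomised and fitting a baseline-constrained mixed model leaves the same people determining the arm effect. It makes the bias larger when loss depends on follow-up drinking.

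A reader might infer that enrolling to 50 per arm must leave fewer than 50 analysed. The documents do not support this. Section 6 (Target Sample Size) and Section 7 state minimums, and so does Section 10: "This process will be repeated until at least 50 eligible participants are enrolled in each study arm". Section 10 (Data Handling and Record Keeping) also gives 191 electronic surveys without explaining the figure. It is compatible with enrolling above 150, and it cannot be read as a loss rate.

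**Conclusion.** The point holds as an inexpensive improvement. The plan selects the analysis set on an event after randomisation and offers no means of judging the consequence for Hypotheses 1 and 3.

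The sizes rest wholly on the assumed loss rates, correlation and logistic slope. For chatbot versus app they are 0.02 to 0.08 SD at slope 1 and about 0.01 to 0.05 SD at slope 0.5. A wider gap of 25% against 10% at slope 1 gives 0.04 to 0.12 SD.

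A reader might infer that the trial will favour the interventions falsely, or that the wrong larger trial would be chosen. Neither is supported. The sign reverses between baseline-dependent loss and the other two mechanisms, and Aim 3 has no numerical threshold that a shift of this size could be shown to cross.

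**What to change.** 1. **Sensitivity analyses.** Keep the completer comparison. Pre-specify sensitivity analyses covering everyone randomised, in the arm assigned, that shift the mean outcome of those lost separately by arm over a stated range, for example 0.5 SD better to 1.0 SD worse. The plan must state the reference point. If it is the prediction from the analysis in item 3, the estimate for each pair is the adjusted estimate + shift1 × loss1 − shift0 × loss0. At 25% against 15% loss the extreme pairs move it by 1.0 × 0.25 + 0.5 × 0.15 = 0.325 SD one way and 0.5 × 0.25 + 1.0 × 0.15 = 0.275 SD the other. Report the pairs at which the conclusion changes. At 25% against 10% loss and slope 1, the shift that returned the estimate to zero was 0.00 SD for baseline-dependent loss and 0.46 to 0.70 SD for the other two mechanisms, inside this range.
2. **Loss.** Report loss by arm, with baseline drinking of those lost and those retained.
3. **Baseline adjustment.** Add ANCOVA. It removes the bias only when loss depends on baseline drinking and does not bring those lost into the estimate, so it does not replace item 1.
4. **Hypothesis 2.** State that the survey-completer restriction does not apply, since usage data do not need the follow-up survey.

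The cost is plan wording and a few extra analyses on data already collected. The drawback is that the result may look less certain.

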The interventions offered in this protocol, although self-administered and delivered via a novel mechanism (smartphones), are consistent in terms of content with interventions for alcohol problems that have research evidence for efficacy (e.g., Relapse Prevention). Further, similar self-administered interventions delivered via smartphone, bibliotherapy and the internet have been shown to be effective in substantially reducing alcohol intake. We have developed procedures to deal with the potential issue of exacerbation associated with participation in this study (see below).

In all studies to date of Step Away (2 with U.S. Veterans and one in New Zealand) and its prototype, the LBMI-A (performed at UAA in 2012), no adverse events have been reported.

4. Study Objectives and Purpose

This project will finalize development of the Step Away chatbot, which has been in process for over a year, and create an improved user interface for the Step Away app. We will then conduct a pilot study that compares three conditions, both Step Away interventions (i.e., smartphone app and chatbot) and a wait-list control condition that will receive the app after a 3-month delay. The trial focus will be on determining if the Step Away chatbot has better user engagement with regard to improved utilization of the features, enhanced intervention fidelity and improved alcohol outcomes compared to the Step Away app. Qualitative interviewing of 10 participants in each intervention group will identify perceptions of each intervention's usability and potential barriers to utilization.

Specific aims:

1. Develop a chatbot version of Step Away that delivers the interventions through an interactive format, and that proactively introduces the intervention features in a texting-based, narrative framework.
2. Conduct a pilot randomized controlled trial with a sample of problem drinkers (N = 150) to identify and compare differences in utilization and alcohol outcome efficacy between the Step Away chatbot, the Step Away app and a wait-list control condition.

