Utilization data will be collected from participants who use either the app or the chatbot. Three variables will be collected to measure utilization: total visits, duration of use, and total active days used. Total visits will be measured by the number of times a participant interacts with a feature of the app or the bot. Duration of use will be calculated as the amount of time in between a participants most recent visit to the app or bot and their date of installing the app or bot. Active days used will be calculated by the number of days a participant interacted with the app or bot. Utilization will be calculated for both app and bot users. Independent sample t-tests will be conducted between the means of each variable to determine if there were significant differences between app and bot users.

Research Question 3: Does utilization of the app or bot influence drinking outcomes?

Hypothesis 3: Utilization of the app or bot will mediate drinking outcomes, in that the higher the utilization of the intervention, the greater reduction of drinking the participant will have between baseline and follow-up

Method: Mediation analysis

Utilization data and TLFB data will be used in this analysis. A mediation analysis will be conducted with group as the independent variable, change in drinking as the dependent variable, and utilization as the mediator. Significant effects of usage on change in drinking will determine if utilization predicts change in drinking for either group. A significant indirect effect will determine if utilization mediates the relationship between group and outcome.

10. Ethics/Protection of Human Subjects

Ethical Standard

The investigator will ensure that this study is conducted in full conformity with Regulations for the Protection of Human Subjects of Research codified in 45 CFR Part 46, 21 CFR Part 50, 21 CFR Part 56, and/or the ICH E6.

Institutional Review Board

The protocol, informed consent form(s), recruitment materials, and all participant materials will be submitted to the IRB for review and approval. Approval of both the protocol and the consent form must be obtained before any participant is enrolled. Any amendment to the protocol will require review and approval by the IRB before the changes are implemented to the study. All changes to the consent form will be IRB approved; a determination will be made regarding whether previously consented participants need to be re-consented.

Informed Consent Process

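### Research Question 1 plans only a three-group by time interaction for each outcome; the between-arm differences that Hypothesis 1, the app-versus-bot question and Aim 3 need are not named and have no planned interval

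*Combined protocol and SAP*

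**What the plan says.** Section 9, Research Question 1, lists six outcomes: USAUDIT, SIP-R, the readiness questionnaire, and three Timeline Followback measures (drinks per day, percentage of days abstinent, heavy drinking days). Baseline and follow-up values "will be compared between app, chatbot, and delay groups". The only inferential step is: "Repeated measures ANOVA will be ran to identify if there is an interaction between time and group". Its stated reading is: "An interaction would indicate a significant difference between app, bot, and delay groups in the difference of their baseline and follow-up drinking data".

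The purposes that this analysis serves are more specific:

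- The research question: "Do participants reduce their alcohol consumption more when using the app or the bot".
- The accompanying prediction (Hypothesis 1), which takes delay as its comparator, is: "Participants using either the app or bot will show a significantly greater reduction in alcohol consumption and alcohol related problems".
- The trial focus in section 4 includes, for the chatbot, "enhanced intervention fidelity and improved alcohol outcomes compared to the Step Away app".
- Aim 2 is to "identify and compare differences in utilization and alcohol outcome efficacy between the Step Away chatbot, the Step Away app and a wait-list control condition".
- Aim 3 lets the pilot choose the next trial. If one intervention is clearly superior, it goes forward against usual care. If the between-group effect is small to moderate, the two interventions are compared in a larger trial.

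For utilization (Research Question 2), a two-arm test is named: "Independent sample t-tests will be conducted between the means of each variable to determine if there were significant differences between app and bot users". No equivalent is named for drinking.

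**The concern.** The planned test and the planned questions do not match. A significant interaction says that the three mean changes are not all equal. Hypothesis 1 asks whether the active arms improve more than delay. The research question asks whether app and bot differ, and Aim 3 needs the size of that difference and its uncertainty. None of these is a named analysis of a drinking outcome, and no confidence interval is planned for any of them.

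Hypothesis 1 can also be read in two ways, as each active arm beating delay or as the two pooled beating delay. These are different contrasts with different power. If the plan does not choose, the choice is made at analysis, with six outcomes in view.

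**Working it through.** **1. What the test is.** With two time points, the group-by-time F-test equals a one-way ANOVA on change scores: 3 − 1 = 2 numerator df and 3n − 3 denominator df. Its null hypothesis is that the three mean changes are equal. It carries no direction and identifies no pair.

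**2. Is a contrast named elsewhere?** In section 9:

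| Need | Where stated | Named analysis on drinking | Interval |
|---|---|---|---|
| Active arms vs delay | Hypothesis 1 | none beyond the interaction | none |
| Bot vs app | Research Question 1; section 4 | none beyond the interaction | none |
| Bot vs app effect size | Aim 3 | none | none |
| Bot vs app utilization | Research Question 2 | t-test (utilization only) | none |

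The Research Question 3 mediation model relates group to change in drinking. Its stated readings are the usage effect and the indirect effect.

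**3. Illustration.** The only document input is the target of at least 50 per arm (section 6, Target Sample Size). That section gives no alpha, power, effect size or SD, so there is no figure to reproduce. Assumed here: 50 analysed per arm, change SD 1, two-sided 0.05. Effects are app/bot relative to delay, with positive meaning more improvement.

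Non-centrality λ = n × Σ(μᵢ − μ̄)²:

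- Both arms better, (0.5, 0.5, 0): the mean is 1/3, the squared deviations are 1/36 + 1/36 + 4/36 = 1/6, so λ = 50/6 = 8.33.
- One arm better, (0.5, 0, 0): the mean is 1/6, the squared deviations are 4/36 + 1/36 + 1/36 = 1/6, so λ = 8.33 again.

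The non-central F with 2 and 147 df gives power 0.727 in both cases. The test cannot separate them. Pairwise tests can. By simulation (1,000,000 draws), among significant interactions:

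| Truth (app/bot) | Interaction rejects | Both arms significantly better than delay | Neither |
|---|---|---|---|
| +0.5/+0.5 | 0.73 | 76% | 0.04% |
| +0.5/0 | 0.73 | 3% | 12% |
| +0.25/−0.25 | 0.59 | 0.1% | 63% |

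In the last row, 97% of the significant interactions do show an app-bot difference. The result is real there, but it answers a different question from Hypothesis 1.

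**4. Precision.** The 95% CI half-width for a pairwise difference in change is t × √(2/n) = 1.976 × √(2/50) = 1.976 × 0.2 = 0.395 SD. With baseline adjustment, the variance relative to change scores is s²(1 − r²)/(1 + s² − 2rs), where s is the follow-up/baseline SD ratio. At an assumed r = 0.5 and s = 1 this is 0.75, so the half-width is 0.395 × √0.75 = 0.342.

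**5. Error control.** With all three arms equal, three pairwise tests at 0.05 give at least one false positive with probability 0.122. Performed only after the F-test rejects, they give 0.050. With two arms equal and the third 0.5 SD away, the gated figure is 0.048.

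**The case against.** A reader might infer more than the documents support.

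- *The interaction test is wrong.* It is not. It is a valid test of equal mean changes, and pairwise tests after it hold family-wise error within an outcome.
- *The contrasts would be invented after seeing the data.* Largely not. Hypothesis 1 fixes the comparator, the direction and the arms in advance, the research question fixes app versus bot, and three arms give only three pairs. What is really open is each arm versus pooled.
- *Harm could be reported as support for Hypothesis 1.* If both arms were 0.5 SD worse than delay, the interaction would also reject with probability 0.73. But section 9 presents all outcomes descriptively, and the arm means would show the direction.
- *Aim 3 would have no bot-versus-app drinking result.* This is too strong. Utilization exists only for app and bot users, so the Research Question 3 model would most naturally give a bot-app effect on Timeline Followback change as a by-product. An effect size could also be computed from reported means and SDs.

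It is also fair to say that a pilot need not power every contrast, and that the percentages above would describe any three-group F-test of this size.

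What stands is narrower. Neither the descriptive means nor the mediation by-product is planned as the answer to Research Question 1, neither has an interval, and the mediation model covers only the Timeline Followback outcomes. The general statement that measures are compared between the groups names no pair.

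**Conclusion.** The point holds as an omission of minor to moderate weight. The planned interaction is valid but does not by itself answer Hypothesis 1, the app-versus-bot question or Aim 3, and section 9 names no between-arm difference or interval on drinking to do so. This follows from the text alone. The figures (0.73 in both scenarios; 76% against 3%) only illustrate it and rest on 50 analysed per arm, a change SD of 1 and two-sided 0.05. The analysis population is those who complete both surveys and no dropout rate is given, so intervals would be wider with fewer completers.

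**What to change.** In section 9, Research Question 1, change the method line as well as the last two sentences, so that the two do not conflict. Suggested wording:

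> For each outcome, follow-up will be modelled on arm and the baseline value of the same measure (ANCOVA). App versus delay, bot versus delay and bot versus app will be estimated with 95% CIs, signed so that positive means more improvement, and reported whatever the overall test shows. Hypothesis 1 is read as each arm versus delay. Significance claims for pairwise differences require the 2-df arm test to reject at 0.05; this controls family-wise error within an outcome, not across the six. The bot versus app estimate and CI will inform Aim 3 as an estimate; a claim of clear superiority on a drinking outcome also requires the overall test to reject.

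The sign rule is needed because benefit is an increase for days abstinent and a decrease for drinks per day and heavy drinking days. The last clause is needed because a bot-app CI can exclude 0 while the overall test does not reject. At +0.25/−0.25 this happens in 0.700 − 0.593 × 0.972 = 0.12 of trials.

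**Alternatives.** If the repeated measures ANOVA is kept, the same three differences in change, with CIs, can follow it; baseline adjustment is an efficiency gain, not a validity repair. If the pooled reading of Hypothesis 1 is meant, plan pooled active versus delay as a single ungated test and label the pairwise tests secondary. Gating the pooled test would lower its power at +0.5/+0.5 from 0.82 to 0.72.

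**Cost.** Wording only; no new data, and the planned software fits the model. The gate lowers app-versus-delay power at 0.5 SD from 0.70 to 0.64 on change scores. Baseline adjustment at an assumed r = 0.5 would bring the gated power to 0.94, 0.78 or 0.68 at SD ratios of 0.7, 1.0 or 1.3; the documents give neither r nor the ratio. Intervals stay wide (about ±0.40 SD of change, or ±0.34 adjusted at r = 0.5 and equal variances). Research Question 1 (adjusted follow-up) and Research Question 3 (change in drinking) would give slightly different bot-app estimates unless Research Question 3 is also baseline-adjusted.
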